9.10 Analysis of Safety Data

Quantitative safety data, including the frequencies of AEs, oral temperatures, use of antipyretics and bronchodilators, and length of hospital and ICU stay, will be summarized using descriptive statistics and frequency distributions. Qualitative safety data will be summarized by frequencies and percentages. All summaries will be presented by overall NasoVAX, NasoVAX cohort, and pooled placebo groups. AEs will be coded using the latest version of MedDRA, and severity will be coded using the latest version of the CTCAE, v.4.0.3. Concomitant medications will be coded using the latest version of the World Health Organization (WHO) drug dictionary. Safety comparisons will be made by treatment group and include comparisons for cohort or stratification factors (ages 35-64 years vs. ages 65 years and above, one or more risk factors present vs. no risk factors present).

9.10.1 Adverse Events

All AEs recorded on the AE eCRF during the study will be coded to SOC and PT using the most current version of MedDRA, currently MedDRA 20.1.

A treatment-emergent AE (TEAE) is defined as an AE that was not present prior to treatment with IP, but appeared following treatment or was present at treatment initiation but worsened during treatment. An AE that was present at treatment initiation but resolved and then reappeared while the patient was on treatment is a TEAE (regardless of the intensity of the AE when the treatment was initiated). Programmatically, an AE will be classified as a TEAE if the start date and time occurs on or after the start date and time of first IP dosing.

All reported AEs will be listed, but only TEAEs will be summarized.

The overall incidence of TEAEs (number and percentage of patients, 95% CI) as well as the number of events will be summarized by treatment group, intensity as assessed by the latest version of National Cancer Institute's Common Terminology Criteria for AEs, SAE, related TEAE, TEAEs leading to study or investigational product discontinuation, and SAEs resulting in death.

The number (percentage, 95% CI) of patients with AEs from Day 1 to Day 42 (including SAEs) will be summarized for each MedDRA system organ class and PT and by treatment group. The number (percentage) of patients with SAEs from Day 1 to Day 210 will be summarized in a similar fashion. The number (percentage, 95% CI) of patients with AEs by severity and by relationship to IP will also be summarized.

The TEAEs will be summarized and tabulated at both the patient (n [%] of patients) and event (number of events) level for each treatment group and overall as follows:

- SOC and PT
- SOC, PT, and maximum reported severity
- SOC, PT, and maximum relationship to investigational product

Subjects with SAEs will also be summarized by SOC and PT for each treatment group and overall.

For the incidence at the patient level by SOC and PT, if a patient experiences more than 1 event within the same SOC and PT, only one occurrence will be included in the incidence.

For the incidence at the patient level by SOC, PT, and severity, if a patient experiences more than 1 event within the same SOC and PT, only the most severe occurrence will be included in the incidence.

For the incidence at the patient level by SOC, PT and relationship to investigational product; if a patient experiences more than 1 event within the same SOC and PT, only the most closely related occurrence will be included in the incidence.

Listings of AEs and SAEs will be provided.

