## STUDY SUMMARY

Sponsor: Altimune, Inc.
Study Title: Phase 2, Double-blind, Randomized, Placebo-controlled Study of NasoVAX in the Prevention of Clinical Worsening in Patients with Early Coronavirus Infectious Disease 2019 (COVID-19)
Study Number: ALT-601-201
Study Phase: 2
Study Centers: Up to 12 centers in the United States
Number of Patients Planned: NasoVAX Approximately 96 patients with early COVID-19 will be enrolled and randomized 1:1 to NasoVAX or placebo in 3 successive cohorts defined by age and risk factors for severe COVID-19 ( Exclusion Criterion 5 ) (Cohort 1, ages 18-49 years and risk factors disallowed; Cohort 2, ages 18 and above and risk factors disallowed; and Cohort 3, ages 18 and above and risk factors allowed) of approximately 20, 28, and 48 patients, respectively, with patients randomized 1:1 to NasoVAX or placebo within each cohort. Cohort 2 will be stratified by age groups of 18-64 years and 65 years and above, whereas Cohort 3 will be stratified by age groups (ages 18-64 years, ages 65 and above) and co-morbidity (one or more risk factors present, no risk factors present).
Duration of Patient Participation: Each patient will participate in the study up to approximately 4 weeks (28 days). Patients who remain hospitalized at the end of 28 days will be followed through Day 42 or death, whichever is sooner.
Enrollment Period: Approximately 3 months

Study Objectives: Efficacy Primary Objective: To assess the effectiveness of NasoVAX in preventing clinical worsening in patients with early COVID-19 Secondary Objectives: 

To assess the effects of NasoVAX on the severity of COVID-19, as indicated by changes in resting peripheral oxygen pulse saturation (SpO2) and resting pulse rate

To assess the effects of NasoVAX on rates hospital admission, oxygen supplementation and mechanical ventilation

*Safety*

Primary Objective

- To assess the safety and tolerability of NasoVAX in patients with early COVID-19

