### **8.3.4 Adverse Events**

The AE reporting period is from the start of study drug administration on Day 1 through Day 14 or until time of hospitalization. AEs will be assessed by direct observation on Day 1 and then by web-based questionnaire and patient interview during daily telephone contact through Day 14 after study drug administration and then through telephone contact thereafter until resolved, stabilized, or transitioned to the patient's main healthcare provider for follow up.

Details on the definitions, reporting, and management of AEs are provided in [Section 9](#).

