After discharge on Day 1, patients will return home for the duration of the study. Patients are to measure resting SpO₂, resting pulse rate, and oral temperature twice daily at 09:00 hours and 16:00 hours, with a 1-hour window around each time point, and at any time they experience worsening symptoms until Day 14 or hospitalization, whichever comes first. Patients are to record COVID-19-related symptoms daily during this same time period. Study center personnel will contact patients daily by telephone during this period to document the patient's clinical status, record concomitant medications and monitor for AEs.

After Day 14, study center personnel will contact patients via telephone approximately every 7±2 days for 14 additional days to determine if they were hospitalized and to follow AEs that were not resolved by Day 14. If the patient is hospitalized at any time, the dates and times of hospital admission/discharge, ICU admission/discharge, and ventilation requirement are to be recorded, as applicable. Patients who remain hospitalized at the end of 28 days will be followed through Day 42 or death, whichever is sooner.

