4.2 Schedule of Events

The schedule for study activities is presented in [Table 2](#).

Confidential

Table 2 Schedule of Events – Screening and Treatment Periods

Procedure	Study Visit Type / Day			
	Screening	Study Drug Treatment	Diary Completion/ Telephone Contact	Telephone Contact
	Study Center Visit		Remote Visit	
	Day 1 Pre-Dose	Day 1	Daily Days 1 to 14	Days 21 and 28 ±2 days
Informed consent	X			
Eligibility criteria check	X			
Demographics	X			
Medical history	X			
Focused cardiovascular and respiratory physical examination	X			
Height and weight	X			
Blood pressure and respiratory rate	X			
Urine pregnancy test ^a	X			
Randomization	X			
Study drug administration ^b		X		
Resting SpO ₂ ^c	X		X ^d	
Resting pulse rate ^c	X		X ^d	
Oral temperature ^c	X		X ^d	
Baseline/Concomitant medications	X		X	X
AEs			X	X
eDiary completion for COVID-19 symptoms ^e	X		X	
Criteria for the Assessment of Severity of Illness in Patients with COVID-19 ^f	X			X
Daily telephone contact to document concomitant medications, clinical and hospitalization status and AEs ^g			X	
Follow-up contact for hospitalization status, COVID-19 outcomes, and AEs ^h				X

^a For women of child-bearing potential only. Results must be available and confirmed to be negative before study drug administration.

^b Study drug is to be administered with the patient in the supine position. The patient is to remain in the supine position for 30 minutes thereafter and be observed for at least 2 hours post intranasal administration.

^c To be measured remotely daily at 09:00 and 16:00 hours or at any time the patient experiences worsening symptoms using the study-supplied devices and recorded in the eDiary. Resting SpO₂ and pulse are to be measured at rest for 2 minutes. A ±1 hour window will be allowed. On Day 1, only the afternoon (16:00 hours) measurement is required and may be measured at the study center or remotely.

^d If the Screening visit occurs in the morning, the patient will be responsible for recording the 16:00 measurements at home later that day; if the visit occurs after 16:00, measurements will commence at home the following morning.

Confidential

- ^e The following symptoms will be recorded: fatigue, chills, headache, cough (with or without sputum production), myalgia, sore throat, shortness of breath, nasal congestion, diarrhea, and nausea or vomiting.

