Blood pressure and respiratory rate obtained after sitting at rest for at least 5 minutes will be recorded at Screening. The procedures for recording resting pulse rate and oral temperature are detailed in Protocol Section 8.2.1.

6.3.4 *Adverse Events*

The AE reporting period is from the start of study drug administration on Day 1 through Day 14 or until time of hospitalization. AEs will be assessed by direct observation on Day 1 and then by web-based questionnaire and patient interview during daily telephone contact through Day 14 after study drug administration and then through telephone contact thereafter until resolved, stabilized, or transitioned to the patient's main healthcare provider for follow up.

Details on the definitions, reporting, and management of AEs are provided in [Section 7](#).

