7.2 Reporting Responsibilities and Periods

It is the responsibility of the Investigator to perform periodic assessment for AEs. AEs spontaneously reported by the patient or reported in response to an open question from the study personnel (eg, ‘Have you had any health problems since the previous visit/you were last asked?’) or revealed by observation will be recorded.

AEs and concomitant medications will be recorded from the start of study drug administration on Day 1 through 14 or until the time of hospitalization. The AE term, date of AE onset, date of AE resolution (if applicable), severity, causality, action taken for the AE, outcome and whether or not the AE was serious will be recorded.

AEs must be monitored until they are resolved or, stabilized or transferred to the patient’s main healthcare provider for follow up., are clearly determined to be due to a patient’s stable or chronic condition or intercurrent illness(es), the patient is hospitalized or follow-up is no longer possible. Data describing AEs will be recorded in the patient’s medical record and as appropriate, an SAE report form. SAEs will be reported to the Sponsor as described in Protocol Section 9.6.

Any SAE that the Investigator considers to be related to study drug and occurs at any time after completion of the study must be reported to the Sponsor or designee. If at the time the Investigator initially reports an SAE, the event has not resolved, the Investigator must provide a follow-up report as soon as it resolves (or upon receipt of significant information if the event is still ongoing).

Note that for the purposes of this study, hospitalization due to worsening fever, cough or shortness of breath, resting SpO₂ or resting pulse rate or symptoms of COVID-19 that are reported at Baseline will not be considered an SAE.

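### SAP 9.10.1 summarizes SAEs to Day 210 and AEs to Day 42, but AE recording ends at Day 14 or hospitalization and no scheduled follow-up runs past Day 42

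*SAP*

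**What the plan says.** SAP 9.10.1 sets two reporting windows. For AEs it asks for the number and percentage, with a 95% CI, of "patients with AEs from Day 1 to Day 42 (including SAEs) will be summarized", by system organ class and preferred term. For SAEs it asks for the number and percentage of "patients with SAEs from Day 1 to Day 210 will be summarized", laid out similarly. Neither sentence names a denominator. The programming rule for a treatment-emergent event in the same section fixes the start (first dosing) but no end.

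The collection rules are shorter. Protocol 8.3.4 states: "The AE reporting period is from the start of study drug administration on Day 1 through Day 14 or until time of hospitalization". SAP 6.3.4 repeats the limit, "through Day 14 or until time of hospitalization". SAP 7.2 says that AEs and concomitant medications "will be recorded from the start of study drug administration on Day 1 through 14 or until the time of hospitalization". Seriousness is one of the items recorded for each AE, and neither document sets a separate, longer period for SAEs.

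After Day 14, SAP 4.1 has site staff telephone patients roughly weekly "for 14 additional days to determine if they were hospitalized and to follow AEs that were not resolved by Day 14". The schedule in SAP 4.2 also marks the AE row at Days 21 and 28 and has a row titled "Follow-up contact for hospitalization status, COVID-19 outcomes, and AEs".

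The Protocol Study Summary puts participation at about 28 days. Patients still in hospital at that point are followed to Day 42 or death, and Protocol 4.1 adds patients readmitted before Day 42. For hospitalized patients, Protocol 8.2.5 and SAP 6.2.5 collect admission, ICU, oxygen, ventilation, ambulatory status and death, but not AEs in general.

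**The concern.** A table headed with a day range tells the reader that the patients in the denominator were watched over that range. Here they were not. Any patient with no event on file would count as event-free to Day 42 or Day 210, although event recording had stopped at Day 14 or earlier and contact had normally stopped at Day 28.

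This matters because safety is a primary objective in the Protocol Study Summary, and both sample-size sections describe the study as an assessment of initial safety. A low SAE percentage headed Day 1 to Day 210 would read as about seven months of reassurance about the product. The data could support a statement about roughly the first two weeks, with partial information to Day 28.

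**Working it through.** **Step 1. Can Day 210 be reached from any follow-up limit in the documents?** The candidates are:

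| Limit | Source | Last day | Short of Day 210 | Share of 210 days | Share of 42 days |
|---|---|---|---|---|---|
| AE recording | Protocol 8.3.4; SAP 6.3.4, 7.2 | 14 | 210 − 14 = 196 | 14/210 = 6.7% | 14/42 = 33.3% |
| Last scheduled call | SAP 4.1 (14 + 14) | 28 | 210 − 28 = 182 | 28/210 = 13.3% | 28/42 = 66.7% |
| Last call, end of window | SAP 4.2 (28 + 2) | 30 | 210 − 30 = 180 | 30/210 = 14.3% | 30/42 = 71.4% |
| Still in hospital at Day 28, or readmitted | SAP 4.1; Protocol 4.1 | 42 | 210 − 42 = 168 | 42/210 = 20.0% | 42/42 = 100% |

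None gives 210. The limit on concomitant-medication documentation (30 days after dosing, SAP 4.7) falls at about the same point as the third row. Arithmetically 28 + 182 = 210, which is about six months after the last call, but no contact is scheduled in that interval. The only six-month period tied to participation is in Exclusion Criterion 9 (Protocol 5.3), which is an eligibility rule. Day 210 appears nowhere else in either document.

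**Step 2. Size of the Day 210 gap.** The window is 210/14 = 15 times the AE recording period and 210/28 = 7.5 times nominal participation. It ends 168 days after the last scheduled follow-up of any patient.

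**Step 3. The Day 42 AE window.** For a patient who stays out of hospital, recording ends 42 − 14 = 28 days before the window closes, and contact ends 42 − 28 = 14 days before. A patient who is followed to Day 42 has been hospitalized, and AE recording stopped at admission or at Day 14, whichever came first. So the window exceeds AE recording for every patient, including those whose hospital course is followed to Day 42.

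**Step 4. What a percentage would mean (illustration only).** Assume no SAEs among the 48 planned NasoVAX patients (SAP Table 1). The upper 95% Clopper-Pearson limit is 1 − 0.025^(1/48) = 7.4%. That limit describes the period in which SAEs were recorded, about 14 days. It says nothing about the risk from then to Day 210. The zero count is hypothetical, and the Day 210 sentence does not itself ask for a confidence interval.

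**The case against.** The case for leaving the text alone has several parts.

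*Later events are sought.* The schedule marks AEs at Days 21 and 28, and the Appendix B script asks about hospital admissions and about health changes that needed a doctor's visit. This stands in part. A reader might infer from the Day 14 text that nothing is learned afterwards, and that is too strong. A reader might equally infer that SAEs are collected to Day 28, but no section sets such a window and the text limits these calls to hospitalization and unresolved AEs. Schedule and text conflict and need reconciling. Even the generous reading stops at Day 28.

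*Late SAEs can reach the sponsor.* SAP 7.2 requires related SAEs to be reported whenever they occur after the study, and pregnancies are followed to completion. True, but this reporting is passive or selective. It can yield isolated cases, not an incidence of all SAEs in all treated patients.

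*Day 42 is a real limit in this trial.* It is the outer follow-up limit and the mortality horizon, so it is a much milder mismatch than Day 210. That stands. But mortality is an efficacy endpoint, deaths from worsening of the COVID-19 symptoms reported at Screening are not SAEs (SAP 6.2.6), and general AE recording has stopped by then.

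*The SAP prevails.* SAP 9.13 gives it precedence over the protocol. Precedence cannot supply data that were not collected, and SAP 9.10.1 conflicts with the SAP's own sections 6.3.4 and 7.2.

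*Little changes.* The labels alter no event count, both arms share one schedule, and AEs and SAEs are also listed. This largely stands: the documents give no basis for saying that the labels bias the comparison between arms. What is misstated is the period to which each percentage refers.

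**Conclusion.** The mismatch is real. Day 210 has no support in either document and lies 168 days beyond any scheduled follow-up. The Day 42 AE window runs 28 days past AE recording for every patient. Tables built as written would label a period of about 14 days, partly extended by the later calls, as 42 or 210 days.

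The statement that unobserved patients would count as event-free assumes that all dosed patients form the denominator. That is the natural reading of the Safety Analysis Set in SAP 9.5, but SAP 9.10.1 does not say so.

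Two stronger readings should be avoided. One is that the SAP would publish a 7.4% upper limit as a 210-day risk; the Day 210 sentence specifies a number and percentage only, so that figure is illustrative. The other is that Day 210 was carried over from another study's plan; the documents do not show where it came from.

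This should be corrected before database lock. It is an error in the stated reporting window, not a flaw in the design.

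**What to change.** In SAP 9.10.1:

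- Remove the Day 210 window. If longer SAE follow-up was in fact intended, it would need a collection period and contacts in the protocol, not just a table label.
- Replace the Day 42 AE window with the actual collection period: treatment-emergent AEs and SAEs from Day 1 through Day 14 or hospitalization.
- Tabulate or list separately, labelled as such, events learned at the Day 21 and Day 28 calls, deaths through Day 42, and related SAEs reported after the study.
- Name the denominator of each table and state the observed follow-up behind it.

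Reconcile the AE marks at Days 21 and 28 in both schedules with the Day 14 text, so that it is clear whether a new event first reported at those calls is recorded as an AE.

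Do not add a Day 29 to 42 AE incidence table among hospitalized patients. Apart from deaths it would have almost no AE data behind it. Its denominator would also be defined by being in hospital, an outcome after randomization and part of the primary endpoint, so the arms would no longer be comparable as randomized.

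The cost is SAP wording, revised table shells and one clarification of the schedule. No new data are needed.

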7.3 Assessment of Adverse Events

7.3.1 Severity

The Investigator should assess the severity of each AE. The AE will be recorded at its initial severity level. The initial AE will be considered ended and a new AE will be recorded if the event changes in severity.

The severity of all AEs, both serious and non-serious, will be assessed by assigning a grade of 1, 2, 3, 4, or 5 according to the latest version of Common Terminology Criteria for Adverse Events (CTCAE).

When an AE cannot be graded by CTCAE, the following severity grading may be used:

- Grade 1 (Mild): awareness of sign or symptom, but easily tolerated
 - Grade 2 (Moderate): discomfort enough to cause interference with usual activity
-

- Grade 3 (Severe): incapacitating with inability to work or do usual activity
- Grade 4 (Life-Threatening): refers to an event in which the patient was, in the view of the Investigator, at risk of death at the time of the event. (This category is not to be used for an event that hypothetically might have caused death if it were more severe.)
- Grade 5 (Fatal): death related to AE

An AE that is assessed as severe should not be confused with an SAE. Severity is a category for rating the intensity of an event, and both non-serious AEs and SAEs can be assessed as severe. An event will be defined as serious when it meets one of the criteria described in Protocol Section 9.1.3.

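### Minor: the event-level TEAE counts in SAP 9.10.1 count one continuous episode once for every grade it passes through, because each severity change opens a new AE record

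*SAP*

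**What the plan says.** The recording rule is the same in Protocol 9.3.1 and SAP 7.3.1. Each AE holds a single grade: "The AE will be recorded at its initial severity level". When that grade moves, "The initial AE will be considered ended and a new AE will be recorded if the event changes in severity". The rule gives no direction, so improvement triggers it as well as worsening.

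SAP 9.10.1 then reports event counts in two places. In the overall TEAE summary, patient numbers and percentages "as well as the number of events will be summarized by treatment group", with breakdowns that include intensity, seriousness and relatedness. The TEAE tables are "tabulated at both the patient (n [%] of patients) and event (number of events) level for each treatment group and overall", by SOC and PT, by maximum severity, and by maximum relationship.

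Treatment emergence is decided by start time: "an AE will be classified as a TEAE if the start date and time occurs on or after the start date and time of first" dosing.

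The section has three once-only rules. The first opens "For the incidence at the patient level by SOC and PT, if a patient experiences more than 1 event within the same SOC and PT", and the other two have the same patient-level scope. For severity, "only the most severe occurrence will be included in the incidence"; for relationship, "only the most closely related occurrence will be included in the incidence". The one other rule against duplication, in SAP 9.10.2, drops AE-log events that the eDiary also captured.

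**The concern.** A reader of a safety table takes the number of events to mean the number of separate adverse events. Under these rules it is the number of severity-specific records. An event that begins at Grade 2 and settles to Grade 1 before resolving is entered twice. The second entry exists only because the patient improved, yet it starts after dosing and so is flagged as treatment-emergent.

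Two outputs suffer. The total and the SOC/PT event counts depend on how often grades moved as well as on how many events occurred. The event-level severity table spreads one episode over several grade rows, so its maximum-severity label no longer describes it.

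Safety and tolerability is the primary safety objective. The SAP presents results by NasoVAX cohort (10, 14 and 24 patients), so a few patients with fluctuating events could make up much of a cohort's event count. Daily telephone contact to Day 14 gives regular opportunities to record a change of grade.

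**Working it through.** The plan states no figure on this point, so there is none to reproduce. The check applies the recording rule and then the counting rules.

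**Inputs from the documents**
- One grade per AE record, and a new record at each severity change (Protocol 9.3.1, SAP 7.3.1).
- Event counts overall and by SOC/PT, severity and relationship (SAP 9.10.1).
- TEAE flag set by the start time of the AE (SAP 9.10.1).
- Once-only rules at patient level only (SAP 9.10.1).

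**Step 1: one episode.** Records per episode = 1 + number of grade changes.

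| Grade course | Changes | Events counted | Patients counted | Entries by grade row |
|---|---|---|---|---|
| 1 | 0 | 1 | 1 | Grade 1: 1 |
| 2-1 | 1 | 2 | 1 | Grade 2: 1; Grade 1: 1 |
| 1-2-1 | 2 | 3 | 1 | Grade 1: 2; Grade 2: 1 |
| 1-2-3-2-1 | 4 | 5 | 1 | Grade 1: 2; Grade 2: 2; Grade 3: 1 |

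If the records of an episode were joined, each row would count as one event, at Grades 1, 2, 2 and 3 respectively.

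**Step 2: a whole table.** If a share s of episodes each have k grade changes and the rest have none, events counted / true episodes = 1 + s × k. Neither s nor k can be derived from the documents. The values below are assumptions that show the range.

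| s | k | Ratio |
|---|---|---|
| 10% | 1 | 1 + 0.10 × 1 = 1.10 |
| 25% | 2 | 1 + 0.25 × 2 = 1.50 |
| 50% | 2 | 1 + 0.50 × 2 = 2.00 |
| 50% | 4 | 1 + 0.50 × 4 = 3.00 |

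**Step 3: comparison of arms.** Both arms follow the same rule. If their ratios are equal, the relative comparison of event counts is unchanged and only the absolute counts are too high. A distorted comparison needs different patterns of grade change. For example, with equal true episodes and assumed ratios of 1.50 and 1.10, the counts would differ by a factor of 1.50 / 1.10 = 1.36.

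**Step 4: what is not affected.**
- Patient-level n (%) and their confidence intervals: the once-only rules hold each patient to one per SOC/PT, at the worst grade or closest relationship.
- SAEs by SOC and PT: the SAP tabulates subjects.
- Stopping rules (Protocol 7.2, SAP 5.1.2): the Grade 3 rule counts subjects, the hospitalization and ventilation rules count patients, and the rules on a related SAE or a related Grade 4 or 5 AE are met by a single occurrence, so repeat records add nothing.

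**The case against.** The strongest reply is that the SAP never says an event is a record. The recording rule speaks of an event that changes and an AE that is opened, which can be read as one event with several entries. Two of the tabulation bullets refer to a maximum, which suggests some aggregation. This shows that the sponsor may intend to combine records, but it does not supply a rule. The TEAE flag is applied to each AE by its start time, every stated once-only rule is confined to patient-level incidence, and no section says how successive records would be recognised as one event. A programmer following the text would count records.

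The second reply concerns reach, and it stands. The safety endpoint is the incidence and severity of AEs, and incidence is handled at patient level. No test is planned on event counts. Worsening of COVID-19 symptoms reported at Screening is not an AE (Protocol 9.1.1, SAP 7.1.1), and SAP 9.10.2 removes AE-log events also captured in the eDiary, which covers the symptoms graded daily. AEs are recorded only to Day 14 or hospitalization. Few of the remaining AEs may be regraded often.

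A reader might infer that AE incidence is overstated, that SAEs are double-counted throughout, or that a stopping rule could be triggered by repeat records. The documents support none of these: those outputs count patients or subjects, or need only a single event. A repeated serious event could enter only the event count of the overall summary, and only if its grade changed while AEs were still being recorded and the seriousness flag was carried to the new record.

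A reader might also expect a large inflation. The documents give no frequency of grade changes, so a small one is equally compatible with them.

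**Conclusion.** The point holds as a minor one. As written, the plan counts a continuous episode as 1 + its number of grade changes in the event-level TEAE counts, and it can place one episode in several grade rows. This follows from stated rules, not merely from missing detail. It rests on two assumptions: that each AE entry is counted as one event, which is the plain reading of SAP 9.10.1, and that some counted AEs change grade during follow-up.

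The size is unknown. The assumed cases run from 1.10 to 3.00 times the number of episodes, and the narrowed set of AEs gives no reason to expect the upper end. Conclusions drawn from patient-level safety tables are untouched. The absolute event counts and the event-level severity table should not be read literally until the rule is added.

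**What to change.** Add to SAP 9.10.1, which is the right place because Protocol 10.4 assigns data handling conventions to the SAP:

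*For event counts, successive records of the same preferred term in a patient that continue one episode are counted once. A record continues the previous one if it starts on the day the previous one ends or the day after, and the previous one was closed for a severity change rather than resolved, where the outcome field shows this. The combined event takes the first onset, last end date, highest grade, closest relationship and any seriousness flag. Listings keep the records as entered.*

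Footnote the rule on every table that shows event counts.

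The one-day allowance and the outcome condition are both needed. No section tells sites to give the new record the same date as the end of the old one. Exact date equality could therefore miss true continuations, and dates alone could join separate same-day recurrences.

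The cost is one programming step and a few judgement cases in linking records, to be settled before unblinding. Site recording procedures need not change.
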